11.8 Dose Escalation Rules

When the results from the Day 7 visit for the last subject in a cohort (e.g., Cohort 1) are available safety parameters will be analyzed to determine the overall safety of that dose-level (e.g., 1 mg/kg). If any of the following criteria are met, the corresponding dose-level is not considered “acceptably safe”, and the study will not proceed to the next higher dose group (as the review is blinded, this will be across treatment arms).

- Any SAE that can be possibly, probably, or definitively attributed to the study drug
- Any immediate hypersensitivity or cytokine storm events
- Two or more subjects with asymptomatic positive anti-IgG (rheumatoid factor)
- One or more subjects with positive anti-IgG (rheumatoid factor) with associated rheumatologic symptoms (i.e. arthralgia, myalgia, etc.)
- Two or more subjects across all cohorts experience the same Grade 3 or higher adverse effect that can be possibly, probably, or definitively attributed to the study drug

- Three of the first 10 subjects (30%) experience the same grade 2 or higher adverse effect that can be possibly, probably, or definitively attributed to the study drug or any time thereafter 30% of enrolled subjects have the same grade 2 or higher 'related' AE.
- Two or more subjects across cohorts develop a serum creatinine \geq Grade 2 toxicity (≥ 1.8 mg/dL) or doubled from baseline (whichever is lower)

If any of the above criteria are met at any time, then the medical monitor will evaluate unblinded study data and make a determination about continuation of the study and/or amendment of the protocol.

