3.2 Study Design

This safety and tolerability study of intravenous (IV) SAB-176 consists of up to 4 single dose-levels or cohorts (cohort 1–4) in a double-blind, randomized, placebo-controlled dose-escalating cohort design. Four cohorts of 2–10 subjects each will be administered a single IV dose of SAB-176 or saline placebo. At very low doses, the concern is primarily allergic or T-cell activation/cytokine storm, so small cohort sizes should be utilized. As the target dose is approached, the sample size will increase to increase the likelihood of detecting toxicity events. The cohorts and dose levels are outlined in [Table 1](#).

Table 1: Cohorts and Dose Levels

Cohort	Number of Subjects Receiving SAB-176				Number of Subjects Receiving Saline Control
	1 mg/kg	10 mg/kg	25 mg/kg	50 mg/kg	
1	2				1
2		4			2
3			6		2
4				8	2

The number of subjects dosed will follow the limitations below:

- The first three subjects of each cohort will be dosed every other day (48-hour interval).
- For Cohorts 2–4, 48 hours after the third subject is dosed, up to 3 subjects may be dosed per day, until the cohort is completed, and no more than 8 subjects will be dosed per week.
- For cohorts 2, 3, and 4, additional dosing in the cohort may continue only after the safety committee recommends continuation after reviewing the safety data from the 3 initial subjects of the cohort.
- After the first three in each cohort, subsequent subjects will be observed for at least 4 hours before beginning the next infusion in the next subject.

Table 2. Example of dosing timeline

	Infusion Day								
	1	2	3	4	5	6	7	8	9
Subject 1	X								
Subject 2			X						
Subject 3					X				
Subject 4							X*		

Table 2. Example of dosing timeline (con't)

	Infusion Day								
	1	2	3	4	5	6	7	8	9
Subject 5							X (≥4 hrs post Subject 4)		
Subject 6							X (≥4 hrs post Subject 5)		
Subject 7								X	
Subject 8								X (≥4 hrs post Subject 7)	
Subject 9								X (≥4 hrs post Subject 8)	
Subject 10									X

* Additional enrollment in the cohort may continue only after the safety committee recommends continuation after reviewing the safety data from the three initial subjects of the cohort.

NOTE: Only 1 subject should be infused at any given time. An infused subject should be observed for at least four hours prior to beginning the next infusion.

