10.3 Definitions

Adverse Event (AE): Any untoward or unfavorable medical occurrence in a human subject, that includes any abnormal sign (e.g. abnormal physical exam or laboratory finding), symptom, or disease, temporally associated with the subject's participation in the research, whether or not considered related to the research.

Adverse Reaction (AR): An adverse event that is caused by an investigational agent (drug or biologic).

Suspected Adverse Reaction (SAR): An adverse event for which there is a reasonable possibility that the investigational agent caused the adverse event. 'Reasonable possibility' means that there is evidence to suggest a causal relationship between the drug and the adverse event. A suspected adverse reaction implies a lesser degree of certainty about causality than an adverse reaction, which implies a higher degree of certainty.

Serious adverse event (SAE): Any adverse event that results in one or more of the following outcomes:

- Death
- Life-threatening (i.e. an immediate threat to life) event
- Inpatient hospitalization or prolongation of existing hospitalization
- Persistent or significant incapacity or substantial disruption of the ability to conduct normal life functions
- Congenital anomaly/birth defect
- Medically important event*

*Medical and scientific judgment should be exercised in deciding whether expedited reporting is appropriate in other situations, such as important medical events that may not be immediately life threatening or result in death or hospitalization, but may jeopardize the subject or may require intervention to prevent one of the other outcomes listed above.

Unexpected Adverse Event: An AE is unexpected if it is not listed in the Investigator's Brochure or Package Insert (for marketed products) or is not listed at the specificity or severity that has been observed. It is the responsibility of the IND Sponsor to make this determination.

Serious and Unexpected Suspected Adverse Reaction (SUSAR): A SUSAR is a suspected adverse reaction that is both serious and unexpected.

Unanticipated Problem (UP): Any incident, experience, or outcome that is:

1. Unexpected in terms of nature, severity, or frequency in relation to
 - a. The research risks that are described in the IRB-approved research protocol, informed consent document, Investigator's Brochure, or other study documents; and
 - b. The characteristics of the subject population being studied; and

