11.2 Data and Safety Monitoring

11.2.1 Investigator Safety Monitoring

The Investigator or designee may interrupt the administration of study drug to an individual subject, or enrollment into this study if indicated for unanticipated problems or AEs. In addition, the Investigators are responsible for:

- Protecting the safety and welfare of subjects
- Evaluating subject safety, including physician assessment of AEs for seriousness, severity, and causality
- Notifying the sponsor of SAEs and immediately-reportable events
- Providing detailed written reports, including confirmatory tests promptly following immediate initial reports
- Informing the IRB of SAEs

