11.7 Pausing Rules

If any of the following criteria are met at any time the study will be paused to further enrollment until assessed by the sponsor medical monitor:

- Any SAE as defined in Section 10.3 that can be possibly, probably, or definitively attributed to the study drug
- Three or more subjects in the same cohort experiencing the same Grade 2 or higher adverse effect that can be possibly, probably, or definitively attributed to the study drug
- Two or more subjects develop the same or clinically similar Grade 3 AE or laboratory abnormality
- Two or more subjects develop a serum creatinine \geq Grade 2 toxicity (≥ 1.8 mg/dL)
- Two or more subjects develop \geq 1.5-fold increase in serum creatinine level from baseline
- Two or more subjects develop GFR <70 mL/min, irrespective if serum creatinine is normal range or Grade 1
- Two or more subjects develop a serum creatinine \geq Grade 2 toxicity in PT and/or PTT (i.e. one grade 2 PT and one grade 2 PTT would meet this pausing rule)

The sponsor medical monitor can request information needed (such as a listing of graded AEs) and unblinded randomization scheme (directly from the site investigational pharmacy group) to evaluate the data. For individual subject unblinding, the site will follow their unblinding procedures per SOP-AUSCLN-506. The sponsor medical monitor will ultimately make the decision to either resume the study or stop the study.

If the trial is stopped due to unacceptable adverse events or stopping criteria, the IRB will be notified.

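### Section 11.8 requires a medical-monitor decision after one immediate hypersensitivity or cytokine-storm event but does not hold dosing in the current cohort until it is made, and 11.7 does not list the event

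*Protocol*

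**What the plan says.** Section 11.8 of the protocol lists "Any immediate hypersensitivity or cytokine storm events" with no qualifier for grade, seriousness or attribution. Two consequences follow. At the cohort review, held once the last subject's Day 7 results are in, "the study will not proceed to the next higher dose group". If a criterion is met at any other moment, "then the medical monitor will evaluate unblinded study data and make a determination about continuation of the study".

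Section 11.7 is worded differently. When one of its triggers is met, "the study will be paused to further enrollment until assessed by the sponsor medical monitor". None of its seven triggers names hypersensitivity or cytokine storm.

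Section 3.2 sets the pace. The first three subjects of each cohort are spaced 48 hours apart. In Cohorts 2 to 4, once data from those three have been reviewed, "additional dosing in the cohort may continue only after the safety committee recommends continuation". After that, "up to 3 subjects may be dosed per day, until the cohort is completed", with at least 4 hours of observation between subjects and a weekly cap of eight. Section 11.2.1 adds that the investigator "may interrupt the administration of study drug to an individual subject, or enrollment into this study if indicated for unanticipated problems or AEs".

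**The concern.** Section 3.2 names allergic and cytokine reactions as the main worry at very low doses, and 8.1.1 promises close watch for alpha-Gal hypersensitivity. Yet this is the event for which the protocol demands a decision without stopping dosing until the decision is made. Related SAEs, repeated Grade 3 events and raised creatinine appear in similar form in both 11.7 and 11.8, so they pause the study as well as block escalation. Hypersensitivity appears only in 11.8.

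The case is realistic. Section 8.1.1 offers a horse antitoxin as the nearest comparator, while expecting lower risk with SAB-176. Healthy recipients of that product had no serious reactions, but two had moderate acute allergic reactions that ended the infusion and needed treatment. A like reaction here, if judged non-serious, would fail 11.8 without triggering 11.7. Healthy volunteers, who gain no benefit, could then receive the same dose before the required decision.

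**Working it through.** **Step 1: can one non-serious reaction trigger 11.7?**

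| 11.7 trigger | Subjects needed |
|---|---|
| SAE at least possibly related | 1 |
| Same related effect, Grade 2 or higher, same cohort | 3 |
| Same or similar Grade 3 event | 2 |
| Creatinine Grade 2 or higher | 2 |
| Creatinine up 1.5-fold or more | 2 |
| GFR below 70 mL/min | 2 |
| Grade 2 or higher PT and/or PTT | 2 |

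Only the first can be met by one subject, and it requires an SAE. Under 10.3 that includes a medically important event, one that "may jeopardize the subject or may require intervention to prevent one of the other outcomes listed above". A single reaction judged to fall short of that meets none of the seven.

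**Step 2: which other safeguards act automatically?**

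- The committee gate in 3.2 acts once per cohort, before Subject 4 of Cohorts 2 to 4. It does not stand between Subjects 1, 2 and 3, and Cohort 1 has only three subjects.
- Section 5.3 stops the affected subject's own infusion.
- The 4-hour interval lets a reaction be seen before the next infusion, but no rule turns that into a hold.
- Section 11.2.1 gives the investigator a power, not a duty.
- The escalation block does not reach the rest of the same cohort, and Cohort 4 has no higher dose.

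**Step 3: how many could follow?** Cohort sizes from Table 1 (active + saline) are 2+1 = 3, 4+2 = 6, 6+2 = 8 and 8+2 = 10, which total the planned 27. An event in Subject k of the first three leaves 3 − k subjects before the gate or the end of Cohort 1. From Subject 4 on, it leaves n − k.

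| Event in | Cohort 1 | Cohort 2 | Cohort 3 | Cohort 4 |
|---|---|---|---|---|
| Subject 1 | 2 | 2 | 2 | 2 |
| Subject 2 | 1 | 1 | 1 | 1 |
| Subject 3 | 0 (complete) | 0 (gate) | 0 (gate) | 0 (gate) |
| Subject 4 | n/a | 6 − 4 = 2 | 8 − 4 = 4 | 10 − 4 = 6 |

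In the first two rows the next subject is due at 48 hours. Cohorts 2 to 4 each have 2 saline subjects. Between 0 and 2 of them may fall after Subject 4, so the number still to receive SAB-176 is 0 to 2, 2 to 4 and 4 to 6.

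**Step 4: how fast?** In Table 2, Subject 4 is dosed on Day 7. Subjects 5 and 6 follow that day and Subjects 7 to 9 on Day 8, so 2 + 3 = 5 of the six remaining in Cohort 4 are dosed by the end of the next day. Subject 10 follows on Day 9. If the weekly cap counts any seven days, Days 3 to 9 would hold nine infusions (Subjects 2 to 10), and Subject 10 moves to Day 10.

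**The case against.** The strongest reply is that 11.8 does not wait for Day 7. Its closing sentence applies at any time, covers Cohort 4, and calls for a decision on whether the study continues, which would naturally come before the next infusion. Investigators are charged with subject safety and may interrupt enrollment, only one subject is infused at a time, and the Safety Monitoring Plan and the SRCP, neither of which is shown, may contain a hold. This stands as a reason to expect that someone would act. It does not supply the missing rule: 11.7 shows that the protocol spells out a pause where it means one.

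A reader might infer that dosing could go on after anaphylaxis or a cytokine storm. The documents do not support that. Such an event would ordinarily be life-threatening or medically important under 10.3, its onset during infusion would support at least a possible relation, and one related SAE pauses under 11.7.

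A reader might also treat the first three subjects of Cohorts 2 to 4 as fully covered by the committee. They are not, because the gate holds only Subject 4.

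It is fair to add that no rate supports the scenario. The two antitoxin reactions come without a usable denominator, and whether a similar reaction would be called serious is a judgement.

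**Conclusion.** The point holds in limited form. The protocol requires a decision after one immediate hypersensitivity or cytokine-storm event but does not require dosing in the current cohort to wait for it. The exposed case is a single reaction judged non-serious, in Subject 1 or 2 of any cohort (including Cohort 1) or in Subject 4 or later of Cohorts 2 to 4.

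The largest counts, 2, 4 and 6 further subjects in Cohorts 2, 3 and 4, assume an event in Subject 4 and no action by investigator or monitor. They are upper limits, not expected numbers. A reader might add them up, but they are alternatives: an event in one cohort blocks escalation to the next.

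Confidence is medium, mainly because the two safety plans are not shown. The protocol should still be amended, as a cheap improvement to a safety rule.

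**What to change.** Add to the last sentence of 11.8: *when an immediate hypersensitivity or cytokine-storm event occurs, no further subject is dosed in any cohort, including Cohort 4, until the medical monitor has made the determination.*

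If the event is added to 11.7 instead, that section's pause must be extended to dosing as well as enrollment. Section 3.3 counts a subject as enrolled from the signing of consent, so a pause on enrollment alone does not expressly stop the dosing of subjects who have already consented. The 11.8 clause is the cleaner choice.

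The sponsor may define the event and set a minimum grade, so that trivial reactions do not stop the study. The unblinded evaluation is already required, so the added cost is one clause and perhaps a short delay after a mild reaction, including one on saline, which that evaluation can release.

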Upon review of these package inserts, the development of anti-drug antibodies was noted only in Horse Heptavalent Botulism Antitoxin (11 of 271 subjects). There was no warning in any of these products concerning the development of allergies to other animal proteins, nor of any food allergies. As SAB-176 is a transgenic human IgG, the risk should be even further minimized. However, given the American diet is often heavy in bovine products (milk and/or beef, including derivatives), there is the risk of development of anti-bovine antibodies that is stimulated with repeated exposure. Given the data above and the lack of precedent for the development of food allergies after exposure to similar products, it is anticipated this risk with SAB-176 is very small.

Patients exposed to topical bovine thrombin products (previously used in surgical procedures e.g. fibrin glue) have developed antibodies towards bovine thrombin and contaminating bovine factor V; these antibodies can cross react with human clotting factors and may cause coagulopathy (7). In that series, postoperative coagulation abnormalities were more common in patients with antibodies to human coagulation proteins. SAB-176 clinical lots contain less than 5 ppm (parts per million) of bovine plasma proteins, but the clinical significance of this level of bovine contaminants is not known. Regardless, the serial assessment of PT/PTT in the study will monitor for any coagulation abnormalities in the subjects receiving SAB-176.

As SAB-176 is bovine derived, it may contain galactose-alpha-1,3-galactose (alpha-Gal) glycosylation of the IgG. In other products, the alpha-Gal glycosylation has been shown to be the source of immune based hypersensitivity reactions. For example, the epidermal growth factor receptor (EGFR) inhibitor cetuximab is a monoclonal antibody with alpha-Gal glycosylation. Cetuximab, while a marketed product, has been associated with hypersensitivity reactions, including anaphylaxis. In most subjects that had hypersensitivity reaction to cetuximab, IgE antibodies were present in pretreatment samples (8). This study is designed to start with very small doses, with close monitoring for similar hypersensitivity reactions.

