11.4 Safety Monitoring Plan

PPD has established through their Safety Monitoring Plan a process that defines a committee charged with reviewing the accumulating data as the trial progresses to monitor safety, effectiveness and trial conduct. The Safety Monitoring Plan will be developed by a safety specialist from PPD's pharmacovigilance group. This plan then would be reviewed by the principle investigator, a medical monitor from PPD, as well as medical monitors and subject matter experts (e.g. pharmacokinetic, biostatistics, etc.) identified by the sponsor. While the committee could have up to ten members, including project and study managers, there will be a core committee designated of at least four members that are charged with authorizing study advancement. The plan will be included in the Trial Master File at the end of the study.

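### The Grade 3 escalation criterion in 11.8 counts only identical events, so a related Grade 3 PT plus a related Grade 3 PTT pauses the study under 11.7 but need not hold escalation or compel unblinded review (minor)

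*Protocol*

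**What the plan says.** Two sections of the protocol turn safety findings into action.

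- **11.7 Pausing Rules.** Enrollment pauses until the sponsor medical monitor has assessed the data. One trigger is "Two or more subjects develop the same or clinically similar Grade 3 AE or laboratory abnormality". No attribution to study drug is required. A further bullet covers PT and PTT at Grade 2 or above and pools the two tests: "one grade 2 PT and one grade 2 PTT would meet this pausing rule". On unblinding, "The sponsor medical monitor can request information needed (such as a listing of graded AEs) and unblinded randomization scheme"; the monitor then decides whether to resume or stop.
- **11.8 Dose Escalation Rules.** After the Day 7 results of the last subject in a cohort, a blinded review checks a list of criteria. If any is met, "the study will not proceed to the next higher dose group". The Grade 3 criterion is "Two or more subjects across all cohorts experience the same Grade 3 or higher adverse effect", restricted to effects at least possibly attributed to study drug. If any listed criterion is met at any time, "the medical monitor will evaluate unblinded study data and make a determination about continuation of the study and/or amendment of the protocol".

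The 11.8 list contains no PT/PTT criterion, and nothing in the protocol defines when two effects are the same. Coagulation is a named risk of this bovine-derived product: section 8.1.1 describes antibodies to bovine clotting proteins that cross-react with human factors, and says that "the serial assessment of PT/PTT in the study will monitor for any coagulation abnormalities in the subjects receiving SAB-176".

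**The concern.** The two sections match Grade 3 events by different standards. Under 11.7, similar events count together, and the PT/PTT bullet shows that the authors saw a need to say so for these two tests. Under 11.8, only identical effects count.

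Two subjects with related Grade 3 coagulation abnormalities can therefore be handled in two ways. If both have a prolonged PT, escalation stops by default and the monitor must look at unblinded data. If one has a prolonged PT and the other a prolonged PTT, escalation need not stop under 11.8 and unblinding is left to the monitor. The safety signal is much the same in both cases; the difference lies in which test was abnormal or which term was recorded.

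**Working it through.** The protocol states no operating characteristic for these rules, so there is no figure to reproduce. The check is to trace one case through both lists: two subjects, one with a related, non-serious Grade 3 PT and the other with a related, non-serious Grade 3 PTT.

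**Under 11.7.** The PT/PTT bullet is met, because Grade 3 exceeds Grade 2 and the tests are pooled. The Grade 3 bullet is arguably met as well, through its clinically similar wording. Enrollment pauses.

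**Under 11.8, criterion by criterion.**

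| Criterion | Met by the pair? |
|---|---|
| Related SAE | No, as both events are taken to be non-serious |
| Immediate hypersensitivity or cytokine storm | Not engaged |
| Rheumatoid factor, with or without symptoms | Not engaged |
| Same related Grade 3 or higher effect in two subjects | Not if PT and PTT are separate effects |
| Same related Grade 2 or higher effect in three of the first 10 subjects, or 30% thereafter | No, see below |
| Serum creatinine | Not engaged |

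For the Grade 2 criterion, Table 1 gives cohort totals of 2 + 1 = 3, 4 + 2 = 6 and 6 + 2 = 8 for Cohorts 1 to 3. The three escalation decisions therefore come after 3, 9 and 17 dosed subjects. At 3 and 9, three affected subjects are needed. At 17, 30% is 0.30 × 17 = 5.1 subjects, or three affected among the first 10. Two subjects never reach the count, even if PT and PTT are treated as one effect.

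So no 11.8 criterion is necessarily met. Replace the PTT event with a second PT event and the Grade 3 criterion is met outright.

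**Consequences compared.**

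| | One PT, one PTT (11.7 only) | Two PT (11.7 and 11.8) |
|---|---|---|
| Enrollment paused | Yes | Yes |
| Escalation held by default | No | Yes |
| Unblinded evaluation | At the monitor's request | Required |
| Decision on continuing | Medical monitor | Medical monitor |

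The two routes differ in the second and third rows only.

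No probability is attached to this case. That would need a rate of related Grade 3 PT and PTT abnormalities and the share of subjects with both tests abnormal, and the protocol gives neither.

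**The case against.** The strongest reply is that the difference is a deliberate tier: a sensitive pause and a narrower automatic hold. Several pairs of rules fit that. A 1.5-fold creatinine rise pauses while a doubling holds; a GFR below 70 mL/min pauses only; Grade 2 PT/PTT pauses only; and the Grade 3 pause needs no attribution. Authors who knew how to pool PT with PTT and did not do so in 11.8 may have meant it.

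This stands in part. The protocol does not state such a rationale, and the pattern is not consistent. 11.8 is broader than 11.7 in counting Grade 2 events across cohorts rather than within one, and in listing hypersensitivity, cytokine storm and rheumatoid factor.

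Three further replies stand and limit the point:

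- The 11.8 wording speaks of the same effect, not the same laboratory parameter. A reviewer could treat both abnormalities as one coagulation effect, and the criterion would then be met.
- Either event could be judged medically important and hence an SAE under section 10.3. One related SAE blocks escalation by itself.
- Safeguards remain that do not depend on matching terms. Section 11.4 provides for a "core committee designated of at least four members that are charged with authorizing study advancement"; section 3.2 requires safety committee review after the first three subjects of Cohorts 2 to 4; section 11.2.1 lets the investigator interrupt enrollment; and section 4.8 lets the sponsor terminate the study.

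A reader might infer that such a pair could pass unnoticed into the next dose level, or that subjects are left unprotected. The documents do not support that. The pair pauses enrollment at once, the monitor must assess it, and the monitor can obtain the randomization scheme and stop the study.

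**Conclusion.** The wording mismatch is real and the consequence is minor. For a related Grade 3 pair split across PT and PTT, the protocol as written need not impose the escalation hold or the unblinded evaluation that it imposes for an identical pair. It still imposes a pause and an assessment by the medical monitor, and the committee must still authorize advancement. The loss is a default and a mandatory look at treatment assignment, not detection.

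This rests on three assumptions: PT and PTT are read as separate effects, neither event is serious, and both are judged at least possibly related. If any of the first two fails, 11.8 can be met; if the third fails, an identical pair would not meet the Grade 3 criterion either. It is worth correcting because coagulation is a named risk and the change is small. The documents do not show that the omission was an oversight.

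**What to change.** Amend the Grade 3 bullet in 11.8 only:

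- after *the same*, insert *or clinically similar*;
- after *adverse effect*, insert *or laboratory abnormality (one PT and one PTT count together)*;
- keep the attribution condition;
- state that the medical monitor judges similarity before seeing treatment assignments, so that the judgment is not influenced by them.

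Leave the Grade 2 bullet as it is. Stricter matching is defensible for non-specific lower-grade symptoms.

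The cost is one bullet of text and an occasional extra hold and unblinded review for two events that prove unconnected. The criterion also becomes somewhat more a matter of judgment, but 11.7 already requires the same judgment of similarity.
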